## **Outcome Measure(s)**

- 1) Pain: Both inpatient and outpatient pain scores will be measured using the VAS as documented on the participant study questionnaire.
  - a. am pain score on rising aggregated over 4 days (post-op day 1 –post-op day 4)
  - b. pm (worse pain throughout the day) pain score aggregated over 5 days (post-op day 0 post-op day 4)
  - c. trajectory of am and pm pain scores
- 2) Inpatient opioid pain medication will be collected via the MAR in WakeOne. Outpatient usage will be self-reported in study questionnaire. Inpatient and outpatient total opioid use will be converted to total Morphine equivalent.
  - a. Total morphine equivalent aggregated over day 0-4
  - b. Trajectory of morphine equivalent from day 0 4
- 3) Overall participant satisfaction will be measured on post-op day 4 via participant questionnaire.
- 4) Nurse time will be measured in minutes from time AA nurse enters room to place acupressure pads to when AA nurse exits room. Qualitative questions will be used to assess overall feasibility of nurse initiated auricular acupressure.

| Outcome               | Measure         | Baseline | Post-op Day 1-2 | Post-op days
1-4 |
|-----------------------|-----------------|----------|-----------------|---------------------|
| Pain                  | Visual Analogue | X        |                 | Х                   |
|                       |                 |          |                 |                     |
| Medication            | WakeOne MAR     |          | Х               | Χ                   |
| Inpatient             | Participant     |          |                 |                     |
| -                     | Questionnaire   |          |                 |                     |
| Medication Use | Participant     |          |                 | Х                   |
| Outpatient            | Questionnaire   |          |                 |                     |
| Pellet Retention      | Participant     |          | X               | X                   |
| Days                  | Questionnaire   |          |                 |                     |
| Pain                  | Participant     |          |                 | Х                   |
| Management            | Questionnaire   |          |                 |                     |
| satisfaction          |                 |          |                 |                     |
| Nurse Time            | Questionnaire   |          | X               |                     |
| Nurse Feasibility     | Questionnaire   |          | Х               |                     |

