## **Objectives**

1. To determine if battlefield auricular acupressure applied in the immediate pre-operative period improves post-operative pain management related to:

Protocol version: 5 50CT2020 Template updated 9.24.14

- a. total opioid intake over 5 days
- b. aggregated mean pain score over 5 days
- c. acceptability of auricular acupressure as pain management tool
- 2. To determine the feasibility of nurse initiated battlefield acupressure related to nurse time, cost and perceptions related to auricular acupressure and workflow.

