- Participants may stimulate both ear sites at the same time beginning with site 1 and ending with site 5. Studies have placed acupressure pads for 3-8 days depending on study outcomes (He et al., 2013; Yeh et al., 2014), the pads will be placed for a total of 5 days based on manufacturer's recommendation and the BAA protocol (See example of Earseeds instruction brochure). On the day of surgery, the participant will be informed to apply pressure one to 2 more times that day, depending upon the time the acupressure pads were placed. Participants will be informed that if any acupressure pads fall off while home, they are not to be replaced, but to record on the study questionnaire (see participant questionnaire). Staff nurses will remind participants to complete their questionnaires and to call the AA nurses with any questions related to the acupressure pads or the study.
- At time of discharge, the study personnel will ensure that the participant has participant questionnaire and the addressed and stamped envelope. Instructions for activation of the acupressure pads and questionnaire completion will be reviewed. Participants will be informed that they will either receive a phone call or text reminder twice daily to complete the questionnaire and to activate their pads 3 times per day. Participant is to continue to apply pressure to remaining pads until the end of the study.
- On post-operative day 4, the study personnel will call the patient and instruct them to remove the acupressure pads by gently pulling on the edges of the pad and lifting off with their fingers or using tweezers to loosen the pad if needed. Participants will be reminded to mail questionnaire in the provided postage paid envelope, if they have not done so already
- **Control Group:** The AA nurse will give participants in the control group the study questionnaire once they arrive to the floor and remind participant and family to complete the questionnaire as indicated. At time of discharge, study personnel will ensure that participant has study questionnaire and the addressed and postage paid envelope. Participants will be informed that they will either receive twice daily phone calls or text messages to complete the questionnaire. On postoperative day 4, study personnel will call and remind participate to mail questionnaire in the provided postage-paid envelope.

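### The five-day opioid total adds MAR-recorded hospital use to unverified home self-report by unmasked participants, and the plan neither separates the two nor cross-checks the home part

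*Combined protocol and SAP*

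**What the plan says.** Objective 1a of the combined protocol and SAP is "total opioid intake over 5 days". No outcome is labelled primary, but this one is listed first, and a 25% reduction in analgesia is one of the two targets under Sample Size.

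Outcome Measure(s), item 2, names two sources. For the hospital stay, "Inpatient opioid pain medication will be collected via the MAR in WakeOne". After discharge, "Outpatient usage will be self-reported in study questionnaire". Both are converted to morphine equivalents and combined as item 2a, "Total morphine equivalent aggregated over day 0-4"; item 2b is the trajectory over the same days. The Analytical Plan compares groups by t-test or ANOVA and models morphine equivalents over time with multilevel models. It does not mention analysing the two sources separately. No dispensing record, tablet count or other check of home use is described.

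Under Interventions and Interactions, treated participants wear ten pads and press each one three times a day. Controls receive the questionnaire only, and no sham or masking is described. Both arms are prompted twice daily about the questionnaire; in the treated arm the prompt also covers pad activation. Both arms are telephoned on day 4. In the treatment arm, "On post-operative day 4, the study personnel will call the patient and instruct them to remove the acupressure pads"; in the control arm, "On postoperative day 4, study personnel will call and remind participate to mail questionnaire in the provided postage-paid envelope".

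**The concern.** The total adds a record kept by hospital staff to a diary kept by someone who knows the allocation. If people using the pads report home doses differently from controls, for example because they expect to need fewer, the difference enters item 2a directly. Only the sum is specified, so a reader of the result could not see whether an arm difference arose in hospital, where participant reporting plays no part, or at home, where it is the only source.

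Item 2b is exposed in a second way. Its data source changes from the MAR to the diary at discharge. Arm-dependent reporting that begins at that point would appear in the multilevel model as an arm-by-time effect.

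**Working it through.** **The plan's own figure.** Sample Size gives 24-26 per arm for a 30% pain difference or a 25% analgesia reduction. It states no alpha, sidedness, power or SD, so the figure cannot be reproduced. It can be inverted. With the difference and SD as fractions of the control mean, SD/mean = δ / [(z₁₋α/₂ + z₁₋β) √(2/n)]. Assuming two-sided 0.05 and 80% power:

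- n = 24: 0.25 / (2.802 × √(2/24)) = 0.309
- n = 26: 0.25 / (2.802 × √(2/26)) = 0.322

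The stated size therefore fits an SD of about 0.31-0.32 of the mean, if those assumptions are the ones used. This serves only to set a scale below; the point does not change the sample size.

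**Inputs the documents do not give.** These are the home share of the five-day total (*f*) and the relative under-reporting of home use in the treated arm compared with control (*u*). Both are assumptions here.

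**Bias in the total with no true effect.** Treated home use is recorded as (1 − u) of its true value, so the total falls by the fraction f × u:

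| f | u = 10% | u = 20% | u = 30% |
|---|---|---|---|
| 30% | 3% | 6% | 9% |
| 50% | 5% | 10% | 15% |
| 70% | 7% | 14% | 21% |

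Divided by the 25% target, the corners are 0.03/0.25 = 0.12 and 0.21/0.25 = 0.84; the middle cell is 0.10/0.25 = 0.40. If the treated arm over-reported instead, the sign would reverse and a real reduction would be hidden.

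**Effect on the test.** With 25 per arm, SE = (SD/mean) × √(2/25). The two-sided 0.05 rejection rate with no true effect is Φ(b/SE − 1.96) + Φ(−b/SE − 1.96). For the middle cell, b = 0.10:

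| SD/mean | SE | b/SE | Rejection rate |
|---|---|---|---|
| 0.312 | 0.088 | 1.13 | 0.21 |
| 0.5 | 0.141 | 0.71 | 0.11 |
| 0.8 | 0.226 | 0.44 | 0.07 |

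Over the whole grid the rate runs from 0.05 (b = 3%, SD/mean 0.8) to 0.66 (b = 21%, SD/mean 0.312). The spread shows how little can be said about size from the documents.

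**The case against.** **The magnitude rests on assumptions.** This stands. A reader might take the outcome table's mark for inpatient medication at post-op day 1-2 as the length of stay. That would put 2-3 of 5 days (40-60%) at home and, with 10-20% under-reporting, give a bias of 4-12%. The documents do not support that reading. The same row is also marked under post-op days 1-4 and lists the questionnaire beside the MAR, and no length of stay is stated anywhere. The under-reporting rate has no source in the documents either.

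**A telephoned tablet count is not objective.** This also stands. The same unmasked participant reads out the number. It is more concrete than recall and can be set against a recorded supply, but it does not verify use independently. It can also mislead: Inclusion Criteria admit people with pre-surgery morphine equivalents below 50, so tablets already at home would distort a simple dispensed-minus-remaining figure. The plan does not say that the quantity dispensed is recorded.

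**The parts are not lost.** The sources are named separately and daily values are planned, so the hospital part could be extracted later. That is true, but an unplanned split made after seeing the data carries less weight than a pre-specified one.

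**Prompting is similar in both arms.** Twice-daily questionnaire reminders for everyone limit forgetting and missing entries. They do not address expectation.

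**This is a feasibility pilot, and pain is unmasked self-report too.** The stated purpose is feasibility, which lowers the stakes. But Objective 1 asks an efficacy question and the sample size is framed around detecting an effect. Pain has to be self-reported; opioid use has a recorded component that can be shown separately.

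**The questionnaire is not reproduced.** It may already ask for tablet numbers. Those would still be self-report.

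**Conclusion.** The point holds as a weakness in ascertainment that is cheap to reduce. Home opioid use is self-reported without any described check by participants who know their arm; it is summed with MAR data; and the source changes at discharge within the trajectory.

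The size and direction of any bias are unknown. The 3-21% range is an illustration that depends wholly on an assumed home share of 30-70% and assumed relative under-reporting of 10-30% in the treated arm.

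Two stronger inferences are not supported. One is that a lower total in the acupressure arm would be a reporting artefact: differential under-reporting is plausible, but nothing in the documents shows it. The other is that the day-4 call offers objective verification: it offers a cross-check only.

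**What to change.** 1. In the Analytical Plan, pre-specify the arm comparison of MAR-recorded inpatient morphine equivalents and of home morphine equivalents separately, as well as summed. This needs no new data. Discharge follows randomisation, so show time in hospital by arm beside the two parts.
2. At discharge, record the opioid quantity and strength dispensed and any opioid supply already at home.
3. On the existing day-4 call, ask both arms, with the same script, how many opioid tablets remain, and note the time of the call.
4. Use supply minus remaining as a cross-check on the diary's home total up to the call. Keep the diary for the daily split and for the rest of day 4. The count also preserves a home total up to the call if the mailed diary never arrives.
5. State unmasked self-report of home use as a limitation.

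Cost: a minute or two per call and one chart look-up per participant. Some participants will be unable to count, and the count remains participant-reported. Treatment, visits and sample size are unchanged.

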#### **Analytical Plan**

Results will be analyzed initially using descriptive statistics. Comparison between groups will be done using chi square tests for proportions, and t-tests or ANOVA procedures for continuous variables. Multilevel modeling will be used to determine difference in pain and morphine equivalents over time.

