#### Subjects selection criteria

## Inclusion Criteria

Adults 18-80 admitted for knee or hip arthroplasty. Pre-surgery morphine equivalent < 50, ASA score < 3

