## **Interventions and Interactions**

Terms: AA = Auricular acupressure

Acupressure pad= hypoallergenic adhesive pad containing a 2 mm Vaccaria seeds (Earseeds®) Acupoint = specific area of body where acupressure is applied. BAA= Battlefield Auricular Acupressure

The three regional anesthesia nurses at Davie will be trained to deliver the intervention. All three nurses have been CITI trained and for this protocol will be referred to as auricular acupressure (AA) nurses. In addition to the three AA nurses, CTSI will provide study coordination.

• Training of the AA nurses for auricular acupressure will be done by the Wake Forest Center for Integrative Medicine (CIM) providers. Training will have both didactic and hands-on practice components: basic concepts of auricular acupressure, anatomy and physiology of the ear, assessment of ear anatomy, proper identification of therapeutic acupoints, proper cleaning of the ear, application of acupressure pads and activation, and patient education related to activation of the acupressure pads with manual pressure. Competency will be assessed both by assessment of knowledge (written assessment) and direct observation by CIM acupuncturist of the AA nurse's ability to correctly identify auricular acupressure points through visual inspection, proper application of acupressure pads and activation of the acupressure applied to the acupressure pads.

- Participants will be informed of the study at the time of their surgical consult with their physician or at their pre-operative appointment via flyers made available to the surgical clinics. Prior to the pre-assessment visit, study personnel will review the chart of patients who express interest in the study to confirm eligibility. Informed consent will be obtained at the pre-operative assessment visit by study personnel and the participant questionnaire will be reviewed with instructions on the day of surgery, the AA nurse will confirm consent for participation. Random assignment will be generated by REDCap and emailed to the AA nurse by the study coordinator. If participant is assigned to treatment, the acupressure pads will be placed in the pre-operative holding room. The participant's designee will be given the study questionnaire packet as well as instructions for completing.

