#### Human Subjects Protection

#### **Subject Recruitment Methods**

Several strategies will be implemented to assist with recruitment. Participants may be identified by screening provider schedules. They will be recruited by mailed recruitment letter, myWakeHealth message, telephone, and/or in person when presenting for their surgical consent or pre-operative assessment visit (as allowed by institutional and government policies).

Informational flyers describing the study will be disseminated to the orthopedic clinics at Davie Medical Center. Recruitment will also be done through the orthopedic clinic at the time of a patient's preoperative assessment visit in one of three ways: 1) patients will be given an informational flyer and instructed to call study phone line if interested in participating, 2) they may ask to receive a call from the study team, or 3) they may meet directly with a study team member the day of their pre-operative assessment visit if a study team member is available.

Study personnel will review eligibility questionnaire with participant (confirm age, date of preassessment appointment, date of surgery, type of surgery, presence of pacemaker or other electrical device, hearing aid use, skin disorder or allergies, current medications). If eligible based on phone or in person screen, study personnel will do second stage eligibility screen via WakeOne chart review to calculate current morphine equivalent, medical history for delirium, ASA status, and cognitive impairment or delirium. If eligible, participant will be consented by study personnel at their preassessment anesthesia visit or on the day of surgery. The study personnel will maintain a record of eligible study participants. This list will include name, MRN, surgery type, pre-assessment appointment, and surgery date will be kept in a secure file on a secure computer. The file of eligible participants will be destroyed at the end of recruitment.

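### The opioid and pain comparisons are planned without covariates, although pre-surgery morphine equivalent and joint (knee or hip) are known for everyone before randomisation

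*Combined protocol and SAP*

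**What the plan says.** The Analytical Plan is three sentences long. After descriptive statistics it says "Comparison between groups will be done using chi square tests for proportions, and t-tests or ANOVA procedures for continuous variables", and then "Multilevel modeling will be used to determine difference in pain and morphine equivalents over time". No covariate, baseline adjustment or stratification factor is named for either.

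The opioid outcome under Outcome Measure(s) is "Total morphine equivalent aggregated over day 0-4". Pain is the morning and evening VAS, each aggregated over the follow-up days.

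The Inclusion Criteria are "Adults 18-80 admitted for knee or hip arthroplasty. Pre-surgery morphine equivalent < 50, ASA score < 3". Under Subject Recruitment Methods, type of surgery is confirmed at the eligibility interview, after which "study personnel will do second stage eligibility screen via WakeOne chart review to calculate current morphine equivalent". Both facts are therefore on record before a participant is randomised.

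Allocation is described under Interventions and Interactions as follows: "Random assignment will be generated by REDCap and emailed to the AA nurse by the study coordinator". No stratum or block is mentioned.

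**The concern.** The trial mixes two operations, and it mixes people taking no opioids with people taking up to the eligibility limit. It then sums opioid intake over five days and compares the arms as if nothing were known about anyone beforehand. Pre-surgery morphine equivalent is the outcome variable itself at an earlier time, which makes it the obvious candidate for a prognostic covariate.

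Two things are at stake. First, variance that a covariate could explain stays in the error term and widens the confidence interval. Second, at about 25 per arm, a chance excess of prior opioid users, or of one joint, in one arm can look like an acupressure effect or hide one. With nothing pre-specified, any adjustment made later would be chosen after the data were seen.

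**Working it through.** **Inputs from the document.** 24-26 evaluable per arm, 30 per arm recruited, target differences of 30% in pain or 25% in analgesia (Sample Size); morphine-equivalent limit of 50 (Inclusion Criteria); five outcome days, 0 to 4 (Outcome Measure(s)).

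**Assumed, because not stated.** Two-sided alpha 0.05; 80% power without adjustment; correlation r between covariate and outcome; overall knee share; morphine equivalents per day as the unit of the limit.

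**1. The plan's own sample size.** It cannot be reproduced without alpha, power and SD, so I solved backwards. The standardised difference is d = (1.960 + 0.842) × √(2/n), which is 0.809 at n = 24 and 0.777 at n = 26. A 25% opioid reduction then implies SD/mean of 0.25/0.809 = 0.31 to 0.25/0.777 = 0.32. A 30% pain difference implies 0.37 to 0.39. These figures are implied, not stated.

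**2. Precision.** Adjustment multiplies the residual variance by (1 − r²). Equivalent arm size is n/(1 − r²). Power was recomputed with the noncentral t, starting from 80% at 24 per arm and losing two degrees of freedom:

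| r | Variance removed | 24 per arm acts like | Power |
|---|---|---|---|
| 0.1 | 1% | 24.2 | 80.3% |
| 0.2 | 4% | 25.0 | 81.5% |
| 0.3 | 9% | 26.4 | 83.5% |
| 0.4 | 16% | 28.6 | 86.3% |
| 0.5 | 25% | 32.0 | 89.8% |
| 0.6 | 36% | 37.5 | 93.8% |

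The confidence interval width is multiplied by √(1 − r²), from about 0.95 at r = 0.3 to 0.80 at r = 0.6.

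**3. Knee/hip imbalance without stratification.** This is the exact probability, from two independent binomials, that knee share differs by at least 20 points:

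| Per arm | Knee share 30% | 40% or 60% | 50% |
|---|---|---|---|
| 24 | 15.5% | 18.4% | 19.3% |
| 25 | 16.4% | 19.3% | 20.3% |
| 26 | 9.5% | 11.9% | 12.6% |
| 30 | 12.0% | 14.7% | 15.5% |

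The drop from 25 to 26 is a counting effect: 20 points is exactly 5 people out of 25 but needs 6 out of 26.

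**4. Imbalance in pre-surgery use.** At 25 per arm the standardised difference in a continuous covariate has standard error √(2/25) = 0.283. A gap of 0.5 SD or more, in either direction, has probability 2 × P(Z > 0.5/0.283) = 7.7%.

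Given a gap of exactly 0.5 SD and r = 0.5, the unadjusted difference is shifted by 0.5 × 0.5 = 0.25 SD, or 0.25/0.283 = 0.884 standard errors. Its conditional spread is √0.75 = 0.866. The false-positive rate is P(Z > (1.960 − 0.884)/0.866) + P(Z < (−1.960 − 0.884)/0.866) = 10.8%. A simulation with the t-test gave 10.5%.

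At r = 0.3 the same formula gives 7.2%. With no imbalance it gives 2.4% (r = 0.5) or 4.0% (r = 0.3). These departures average out to 5% over all randomisations.

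**5. Scale of the covariate.** A participant at 49 per day who continued that intake would add 49 × 5 = 245 morphine equivalents to the five-day total, whatever the arm. This is a ceiling for one person, not a typical value.

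**The case against.** The strongest reply is that the planned test is valid. Under randomisation the t-test keeps its 5% error rate, and the 11% figure describes one unlucky draw at one assumed correlation. That is correct. The point is about precision and about the particular trial that will be run, not about validity.

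Next, nothing in the document supports r = 0.3-0.6. If most participants take no opioids before surgery, the covariate will be mostly zeros, r could be low, and a few users would have high leverage. This stands as a limit on the size of the gain, and it makes the normal-theory figures in step 4 approximate. It is a reason to fix the form of the covariate in advance. At r = 0.1 the computed power is still no lower than without adjustment.

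ANOVA procedures and multilevel models can also carry covariates, and the one sentence on REDCap does not exclude strata. True, but none is named, so nothing is pre-specified.

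The study calls itself a feasibility pilot. Objective 1, however, asks whether acupressure improves opioid intake and pain, and the sample size is built on detecting differences in both.

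Finally, neither covariate is the natural baseline for pain. The outcome table marks a baseline VAS, but the pre-placement pain assessment is described only for the treatment group, so it cannot be relied on in both arms as written. The precision argument is therefore strongest for opioid use and weaker for pain. No passage shows that joint predicts either outcome.

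**Conclusion.** The concern holds. The plan pre-specifies no covariate and no stratum, while two candidate covariates are ascertained for everyone before allocation.

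The omission itself is certain from the text. Its size is conditional: a rise from 80% to about 84-94% power if r is 0.3-0.6, and at most about two points if r is 0.1-0.2. A knee-share gap of 20 points or more has a probability of roughly 10-20% for 24 to 30 per arm and knee shares of 30-60%. All power figures assume two-sided alpha 0.05 and 80% power before adjustment. The change should be made because it costs almost nothing, not because the present analysis is invalid.

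**What to change.** 1. **Analytical Plan.** Replace the t-test/ANOVA sentence for these outcomes with, for example: Total morphine equivalent (days 0-4) and aggregated pain scores will be compared between arms by a linear model with arm, pre-surgery morphine equivalent and joint (knee or hip); the same two covariates will enter the multilevel models. Keep the t-test as a descriptive check.
2. **Form of the covariate.** State the unit of the pre-surgery morphine equivalent. Fix in advance whether it enters as a continuous value or, if most values are zero, as any versus none.
3. **Data.** Copy both variables into the analysis data set. Subject Recruitment Methods says the list of eligible participants, which holds surgery type, is destroyed when recruitment ends.
4. **Allocation.** If it has not begun, load a REDCap table with two strata, knee and hip, using blocks within each. If it has begun, leave allocation alone; the model still adjusts for joint.
5. **Baseline pain.** If it is recorded in both arms before allocation, it can be added to the pain models.

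The core change costs one sentence and two residual degrees of freedom (46 to 44 with 48 evaluable). Items 1 to 4 need no new data collection.
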